4. Evaluate the ability of persons with TBI, and their caregivers as indicated, to successfully use abortive headache medications and comply with treatment.
5. Examine the relationship between PTH and cognitive, emotional, and other self-report measures to determine important factors to include in a Phase III study.

VI. Overview of Study Design

This phase II evaluation of sumatriptan as a treatment for PTH will examine the methods and approach necessary to take the next step to a phase III trial. The sample will include 40 individuals with mild (with adequate documentation or in the opinion of study physician), moderate and severe TBI who will be recruited primarily from patients within UWTBIMS and from outpatient clinics and brain injury related organizations to be followed over 3 months. We plan to enroll individuals with moderate to severe headache who experience at least two and up to a maximum of fifteen moderate to severe headaches per month. **Severity will be rated using a 4 point pain scale (0=no headache, 1=mild headache, 2=moderate headache, 3=severe headache).** Headache classification will be confirmed by clinician interview.

Table 1. Summary of Protocol for Proposed Study of Sumatriptan for PTH

Pre-Screening	Visit 1 (Day 1)	Days 1-29	Visit 2 (Day 30)	Days 31-89	Visit 3 (Day 90)
Inclusion/ Exclusion Criteria	Consent Headache questionnaire All subjects trained in use of headache diary	Daily headache diary Weekly telephone calls Daily headache diary reminders (phone, text, email)	Evaluate headache diary for eligibility (pre-visit) Baseline assessment (if meets headache diary eligibility) History, clinical headache interview and physical examination Dispense drug if eligible	Daily headache diary Study drug use per instruction Weekly telephone calls	Follow up Assessment Drug count

Population

A. Inclusion criteria:

A subject will be eligible for enrollment into this study if all of the following criteria are met:

- Age 16-65. The higher age limit is set to 65 to reduce likelihood of health issues which may be a contraindication to the use of sumatriptan and to meet recommendations by the International Headache Society.⁶²

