- History of ischemic heart disease (angina pectoris, history of myocardial infarction, silent ischemia, Prinzmetal's angina/coronary vasospasm, ischemic bowel disease, or peripheral vascular disease) based on self-report or history of basilar or hemiplegic migraine.
- Uncontrolled hypertension at initial visit (sitting systolic pressure > 140 mm Hg, diastolic pressure > 90 mm Hg).
- Impaired renal or liver function by medical history.
- Subject has taken an MAO inhibitor within 2 weeks of screening because these drugs and sumatriptan use the same metabolic pathway.

- Subject has hypersensitivity reactions or other intolerance to sumatriptan or any other 5-HT 1B/1D-receptor agonists.
- If subjects have medication overuse headache in the opinion of the investigator (if using medication to treat acute headache on more than 15 days per month).
- Inability to speak or read English which would limit ability to interact with examiners and complete headache diary and other questionnaires during this study.

C. Sample Size

- This is a single arm, unblinded study and is being undertaken to test necessary study instruments and procedures, establish feasibility and determine side effects in a population with moderate to severe TBI in preparation for a subsequent Phase III study. Therefore, we are using forty subjects as a reasonable sample size to meet these aims.

VII. Overview of Study Procedures

A. Recruitment

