- a. *Physician Health Questionnaire-9 (PHQ-9)⁶⁷,
- b. General Anxiety Disorders 7 (GAD-7)⁶⁸,
- c. * Analog Pain Scale⁶⁹,
- d. Insomnia Severity Index⁷⁰,
- e. *Brief Pain Overview (BPO)⁷¹,
- f. *EuroQol⁷², *Satisfaction with Life Scale (SWLS)⁷³,
- g. *Rivermead Post Concussion Symptom Questionnaire (RPQ)⁷⁴,
- h. Headache Impact Test 6 (HIT-6)⁷⁵,
- i. compliance measures (headache diary completion percentage,
- j. medication counts, reduction in number of headaches and pain relief, number and type of adverse events.
- k. Injury type and severity, medication use, and accompanying disorders.
- l. Data on cognitive status to ascertain appropriateness for participation and to further characterize the population with respect to ability to use headache diary.
 - i. Mini Mental State Examination⁶³,
 - ii. Rey Auditory Verbal Learning Test (RAVLT)⁶⁴,
 - iii. Trail Making Test (TMT)⁶⁵,
 - iv. Wechsler Adult Intelligence Scale – IV (WAIS-IV)

v. Processing Speed Index⁶⁶.

E. Rationale/Explanation for Measure Selection:

Headache relief, frequency and severity are the most frequently used measures of medication efficacy in headache research. The headache survey and HIT-6 will further characterize the headache syndrome and functional impacts of headache. The headache survey will gather information on several factors that will be used to comprehensively describe PTH and its treatment including International Classification of Headache Disorders, 2nd edition (ICHD) criteria (type of headache by characteristics such as location, duration, severity, associated symptoms).⁷⁶ This measure was developed by our group and used for the multi-site study on the natural history of headache after TBI funded by NIDRR through the TBI Model Systems⁵ program and a second single site field-initiated study funded by NIDRR to examine the natural history of headache in individuals with mild TBI.

The **Mini Mental State Examination**⁶³ will be administered at the screening visit. Any score greater than or equal to 25 points (out of 30) indicates a sufficient cognitive level likely to enable a subject to participate without support. A lower score would indicate that the support of a caregiver would likely be necessary for successful adherence to the study protocol.

The other cognitive measures (Rey Auditory Verbal Learning , Trail Making Test, WAIS IV Digit Symbol, and WAIS IV Symbol Search) will be given at the clinic visit on Clinic Visit 2 to characterize the population.

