Pre-treatment Visit (*Visit 1*): Subjects who complete informed consent and meet the inclusion criteria (with no exclusion criteria) will be asked to complete 30 days of headache diary questions. This will document the number of headaches, headache severity, headache days and description of their headache and associated symptoms. This will assist in determining compliance and ability to complete this portion of the study, and ensure that the frequency of headaches is sufficient to include into study intervention (See Attachment 9 Study Sequence Flow Sheet). Research staff will meet with the subject (and caregiver) to provide training on headache diary utilization and will contact them on a daily and/or weekly basis to answer questions and maximize accuracy and compliance with the diary, depending on the subject's preference. Proper utilization of a headache diary and success of data input by the subject and caregiver will be evaluated following weekly interviews with the research assistant. The

headache diary will be available in multiple forms. We will have iPod Touch devices loaded with a headache diary application that will allow for direct entry of responses onto a security protected survey site and will include reminders for daily completion as well as prompts for efficacy of drug treatment used. However for those who prefer, a computer accessed web-based headache diary (otherwise similar to the iPod version) and a paper version with identical questions will be available. For those who choose the alternate forms of diary, a clip-on timer will be provided for recording of headache duration and reminders may be sent as text messages or emails based on subject preference.

Treatment Visit (*Visit 2*):

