Medical History and Physical Examination. A medical history will be obtained at the first visit to review inclusion and exclusion criteria and to elicit a thorough review of systems so that adverse events will be identifiable if they occur. Physical examination at the second visit will also ensure that cardiovascular status is compatible with sumatriptan use and will document current status to allow for identification of potential adverse events. Finally, standard primary headache classification criteria will be reviewed with each patient to determine whether they meet criteria for migraine or probable migraine. The headache diary will be reviewed before the treatment visit is scheduled, and patients who disqualify based on the classification of their headaches will not be scheduled to come in for Visit 2, as this would be an undue and unnecessary burden given they will not be continuing with the study. .

[figure not shown]
Data Collection at Treatment Visit (*Visit 2*): Headache histories will be assessed after 30 days (+/- 3 days), and subjects that have experienced between 4-15 headaches will be included in the medication intervention with sumatriptan. Subjects who qualify for the sumatriptan intervention will receive several assessments, given medication, usage instructions, and scheduled for weekly phone calls for weeks 5-11. (See Table 2). Individuals whose headaches do not meet criteria for migraine or probable migraine, based on data from headache diaries, will have their participation in the study end and will not participate in Visit 2. This is due to the lack of evidence that sumatriptan is effective for the treatment of non-migraine types of headache.

Weekly Telephone Follow-Up Calls: Research staff will call each participant weekly to check on compliance with drug diary use during the first month of the study (Weekly calls 1-3) to check on compliance in diary usage. For weekly calls in weeks 5-11 (for the intervention participants), research staff will inquire about study drug usage, and query for adverse events. Use of rescue medications for headache will be recorded. In the case of minor adverse effects which are bothersome to the patient, the dosage will be decreased to a ½ pill per use.

Follow up Visit (Visit 3). This will be the final visit for the subjects. Vital signs will be obtained. Drug containers and headache diaries will be collected from all subjects. Measures administered on this visit will include:

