- 1) **Interim medical history form** (new diagnoses, changes in medications)
- 2) **Headache Survey**
- 3) **Headache Impact Test (HIT-6)** – Questions about headaches and how much they affect patient’s life.
- 4) **Satisfaction with Life Scale (SWLS)** – Questions about how satisfied patient is will life.
- 5) **Rivermead Post-Concussion Symptoms Questionnaire (RPQ)** – Questions about the 16 most common symptoms after concussion.
- 6) **Patient Health Questionnaire (PHQ-9)** – Questions about symptoms of depression.
- 7) **Brief Pain Overview (BPO), Analog Pain Scale** - Questions asking about pain.
- 8) **Insomnia Sleep Index (ISI)** – Questions about sleeping habits.
- 9) **Euroqol** – Questions about quality of life.
- 10) **Brief Symptom Inventory** – Questions about other symptoms.

Figure 3: Subject Participation Summary

Subject Instruction: During the Visit 1, research staff will explain headache diary and demonstrate usage to ensure patient (and caregiver if present) understand. Instructions will include how and when to take the study medication. Their pain will be assessed 2 hours following use of sumatriptan, this will include:

1. pain presence
2. severity throughout the first 24 hours after use of the study drug
3. whether there was a need for 2nd dosage of sumatriptan
4. Whether there was any use of any rescue medications
5. Whether there was recurrence of pain.

Written and verbal instructions will be given on which drugs to avoid during the study, acceptable drugs to use for rescue therapy, and what to do in the case of an adverse event.

IX. Treatment with Sumatriptan Procedures

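### The 2-week MAO-inhibitor exclusion is counted from screening, about a month before sumatriptan is dispensed, so it does not secure the 2 weeks before first exposure

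*Combined protocol and SAP*

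**What the plan says.** The MAO-inhibitor exclusion in section VI.B reads: "Subject has taken an MAO inhibitor within 2 weeks of screening because these drugs and sumatriptan use the same metabolic pathway".

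Several places fix what screening means and when the criteria are applied:

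- Section VII.E says the Mini Mental State Examination "will be administered at the screening visit", and Table 2 puts that test at Clinic Visit 1.
- Section VIII, Pre-treatment Visit (Visit 1), says that consenting subjects who "meet the inclusion criteria (with no exclusion criteria) will be asked to complete 30 days of headache diary questions". The exclusions are therefore settled before the run-in begins.
- Section VIII, Medical History and Physical Examination: "A medical history will be obtained at the first visit to review inclusion and exclusion criteria".
- Table 1 lists the inclusion and exclusion criteria under pre-screening, before Day 1.

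Drug comes later. Table 1 has "Dispense drug if eligible" under Visit 2 (Day 30), and sections IX and XVI also give Day 30. On timing, section VIII says: "Headache histories will be assessed after 30 days (+/- 3 days".

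The protocol has other provisions on interacting drugs. Section VIII, Subject Instruction, which opens with Visit 1, states: "Written and verbal instructions will be given on which drugs to avoid during the study". Section XVI promises a list of prohibited drugs and excludes people who are on medication likely to interact. Section XIV has the study physician review a current medication list. Table 1 includes a history at Visit 2.

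**The concern.** The interval has a pharmacological reason, which the criterion itself states. That reason concerns the time before sumatriptan is taken. No sumatriptan is given at screening, and a month of diary keeping lies between screening and dispensing. The 2 weeks are therefore counted from the wrong event for their stated purpose.

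Elsewhere the protocol does place safety checks at treatment entry. For the heart it says: "Physical examination at the second visit will also ensure that cardiovascular status is compatible with sumatriptan use". Table 2 puts the pregnancy test at Visit 2. The MAO-inhibitor interval has no equivalent.

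What is at stake is a narrow safety matter. Taken on its own, the criterion would pass a subject whom its own rationale says should not yet be dosed. Sample size, the paired comparison and the effect estimate are not touched.

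**Working it through.** The plan gives no figure to reproduce. The check is a count of days.

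**Inputs**

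- Look-back: 2 weeks = 14 days, dated from screening (section VI.B).
- Screening: Day 1, Visit 1 (section VII.E with Table 2; section VIII). If pre-screening is meant, the date is earlier and the gap wider.
- Dispensing: Day 30 (Table 1; sections IX and XVI), with a window of 3 days either way (section VIII), so Day 27 to Day 33. Dispensing is the earliest point at which a subject can take the study drug.

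**Gap from screening to dispensing**

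30 − 1 = 29 days; with the window, 27 − 1 = 26 to 33 − 1 = 32 days.

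**Days that need to be clear**

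The 14 days before dispensing on Day *d* are Days *d* − 14 to *d* − 1. The table shows how many of them the criterion covers under three readings of its wording.

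| Dispensing day | 14 days before it | (a) 2 weeks before Visit 1 (ends Day 1) | (b) 2 weeks either side of Visit 1 (ends Day 1 + 14 = Day 15) | (c) Screening runs to the Visit 2 decision |
|---|---|---|---|---|
| 27 | Days 13–26 | 0 of 14 | 3 of 14 (Days 13, 14, 15) | 14 of 14 |
| 30 | Days 16–29 | 0 of 14 | 0 of 14 | 14 of 14 |
| 33 | Days 19–32 | 0 of 14 | 0 of 14 | 14 of 14 |

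Reading (a) is the most direct. Reading (b) is generous, because a check on Day 1 cannot verify use over the following fortnight. Reading (c) closes the gap, but the text does not say it.

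**Who is left exposed**

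A subject who passes at Visit 1 and takes no MAO inhibitor afterwards is at least 14 + 29 = 43 days clear on Day 30 (14 + 26 = 40 to 14 + 32 = 46 with the window). The gap therefore concerns only MAO-inhibitor use after screening. With Visit 2 on Day 30, the residual case is use on any of Days 16–29, stopped before Day 30 and not picked up at the Visit 2 history. The documents give nothing from which to estimate how many of the 40 subjects this could be.

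**The case against.** The strongest reply is that the count tests one clause in isolation. The entry exclusion works alongside drugs-to-avoid instructions given from Visit 1 for the whole study. If that list names MAO inhibitors and the subject complies, the two together cover Day 1 to dispensing without a break, and the subject is 40 to 46 days clear. Visit 2 is also an eligibility gate: Table 1 makes dispensing conditional on eligibility and includes a history and physical examination, and the study physician reviews a medication list. For harm to be possible, a subject must start or resume an MAO inhibitor in the run-in, stop before Visit 2, and be missed there.

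Screening may also be meant as a longer process. Table 2 lists the month-long diary and the Visit 2 pregnancy test under initial screening measures, and section VI.A has subjects consent to screening activities, with treatment-phase entry depending on the diary.

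Much of this stands, and it is why the risk is small. It does not remove the point. Re-applying the criterion at Visit 2 does not help while its wording points back to screening. The medication list and the interaction exclusion are framed around current use, so a drug stopped some days earlier may not show. The contents of the drugs-to-avoid list are not in the documents, so whether it names MAO inhibitors can be neither confirmed nor ruled out. The longer reading of screening is possible, but sections VII.E and VIII favour Visit 1, and coverage should not turn on an undefined word.

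**Conclusion.** The point holds as a minor correction to safety wording. On the most direct reading, the criterion covers 0 of the 14 days before dispensing anywhere in the Visit 2 window. Even the generous two-sided reading reaches at most 3 of 14. No provision states a 2-week look-back at dispensing.

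This rests on screening meaning Visit 1 or earlier; if it was meant to run to the Visit 2 decision, there is no gap and only the wording needs clarifying. The practical risk is small because it requires MAO-inhibitor use during the run-in that escapes the other checks. The number affected is probably very small, and no effect on the study's results is claimed. It is worth considering because the change is cheap and the protocol is meant to prepare a Phase III trial.

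**What to change.** Reword the criterion in section VI.B to: no MAO-inhibitor use within 2 weeks before study drug is dispensed (Visit 2) or during treatment. Then:

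- keep the question at pre-screening, so that continuing users do not start the run-in;
- confirm it at the existing Visit 2 medication review, asking about the past 2 weeks as well as current use, before drug is handed out;
- make sure the existing drugs-to-avoid list names MAO inhibitors.

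The cost is one reworded line and one check at a review that already takes place. The downside is that a rare subject may be lost after completing the run-in month, but that is a subject whom the protocol's own reasoning would not dose. In the other direction, someone who stopped in the 2 weeks up to Visit 1 would no longer be barred; with a last dose as late as Day 1 they would be 26 to 32 days clear at dispensing, beyond the 14 required.
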